2.2 Secondary

2.21 Compare progression free survival at 12 months for Grade III patients after radiation therapy targeting volumes designed with both ^{18}F -DOPA PET and conventional MR image information with historical controls from Mayo Clinic Rochester patients, including those on NCCTG clinical trials.

2.22 Compare patient overall survival after radiation therapy targeting volumes designed with both ^{18}F -DOPA PET and conventional MR image information with historical controls from Mayo Clinic Rochester patients, including those on NCCTG clinical trials.

2.23 Evaluate quality of life after radiotherapy treatment targeting dose escalated volumes defined to include high ^{18}F -DOPA PET uptake.

2.24 Determine acute and late effect toxicity after radiotherapy treatment targeting dose escalated volumes defined to include high ^{18}F -DOPA PET uptake.

2.25 Compare confirmed-progression free survival at 12 months for Grade IV MGMT Methylated patients after radiation therapy targeting volumes designed with both ^{18}F -DOPA PET and conventional MR image information with historical controls from Mayo Clinic Rochester patients, including those on NCCTG clinical trials.

2.26 Compare confirmed-progression free survival in grade IV MGMT un-methylated patients with similar historical controls from Mayo Clinic Rochester patients, including those on NCCTG clinical trials.

2.27 Compare confirmed-progression free survival in grade IV MGMT methylated patients with similar historical controls from Mayo Clinic Rochester patients, including those on NCCTG clinical trials.

2.3 Correlative Research

2.31 Compare RT treatment volumes defined by MR only with RT treatment volumes defined with both PET and MR information for Grade IV glioma patients.

2.32 Compare timing of accurate identification of progression defined by ^{18}F -DOPA PET, pMRI and conventional MRI for Grade IV glioma patients.

2.33 Compare patterns of failure after radiation therapy targeting volumes defined with target volumes designed to with both ^{18}F -DOPA PET and conventional MR image information with patterns of failure for historical controls from Mayo Clinic Rochester patients, including those on NCCTG clinical trials.

- 2.34 Compare RT treatment volumes defined by MR only with RT treatment volumes defined with both PET and MR information for Grade III glioma patients.
- 2.35 Evaluate intra- and inter-observer variability with vs. without the addition of ^{18}F -DOPA PET uptake for radiotherapy target volume delineation.
- 2.36 Compare timing of accurate identification of progression defined by ^{18}F -DOPA PET, pMRI and conventional MRI for Grade III glioma patients.
- 2.37 Compare predictive capabilities of ^{18}F -DOPA PET, pMRI and DTI for localization of recurrences for patients treated with ^{18}F -DOPA PET-guided RT dose escalation.

3.0 Patient Eligibility

3.1 Inclusion Criteria

- 3.11 Age ≥ 18 years.
- 3.12 Histologically confirmed newly diagnosed grade IV malignant glioma.
Note: as of addendum 8, Grade III patients are no longer being enrolled.
- 3.13 CT simulation, immobilization, MRI and PET imaging, treatment planning, and all follow-up MRI and PET scans to be performed at Mayo Clinic Rochester.
Note: The actual radiation therapy treatments and follow-up other than imaging can be performed at Mayo Clinic Rochester, Northfield, LaCrosse, Mankato, Eau Claire, or Albert Lea.
- 3.14 Provide written informed consent.
- 3.15 Ability to complete questionnaire(s) by themselves or with assistance.

3.2 Exclusion Criteria

- 3.21 Patients diagnosed with anaplastic oligodendroglioma
- 3.22 Unable to undergo MRI scans with contrast (e.g. cardiac pacemaker, defibrillator, kidney failure).
- 3.23 Unable to undergo an ^{18}F -DOPA PET scan (e.g., Parkinson's Disease, taking anti-dopaminergic, or dopamine agonist medication or less than 6 half-lives from discontinuance of dopamine agonists).

NOTE: Other potentially interfering drugs: amoxapine, amphetamine, benztrapine, bupropion, buspirone, cocaine, mazindol, methamphetamine, methylphenidate, norephedrine, phentermine, phenylpropanolamine, selegiline,

paroxetine, citalopram, and sertraline. If a patient is on any of these drugs, list which ones on the On-Study form.

- 3.24 Any of the following:
- Pregnant women
 - Nursing women
 - Men or women of childbearing potential who are unwilling to employ adequate contraception

4.0 Test Schedule

Tests and procedures	Active Monitoring				
	Baseline				Until PD or patient refusal
	≤21 days prior to registration	Cycle 1 Pre-RT Scans	Cycle 1 RT	Cycle 2 Post RT Scans ⁵ ≤42 days after RT	At every clinically indicated follow-up MR scan (end of each new cycle)
Physical exam, wt, ECOG PS	X				
Neuro history and exam	X			X	X
MMSE ⁴		X ¹²		X	X
CT simulation for radiotherapy planning	X ^{8,9}				
Pregnancy test		X ^{1,R}		X ^{1,R}	X ^{1,R}
¹⁸ F-DOPA-PET ^R		X ⁸		X	X ³
MRI with contrast/ RANO Assessment		X ^{6,8}		X	X ³
Advanced MRI		X ^{7,8}		X	X ³
¹⁸ F-DOPA adverse event assessment		X ²		X ²	X ²
Adverse event assessment ¹¹ (See Section 10.3)	X		X ¹⁰	X	X
QOL assessment ⁴		X ¹²		X	X
Concurrent Steroids and Anticonvulsants		X ¹²		X	X
MGMT Methylation Status	X ¹³				

1. For women of childbearing potential only. Must be done ≤48 hours prior to injection of study drug. Note: For a positive pregnancy test prior to the pre-RT ¹⁸F-DOPA injection the patient will not undergo the ¹⁸F-DOPA PET scan and will instead be taken off study with no follow-up. For any post-RT ¹⁸F-DOPA injection, the patient will not undergo the ¹⁸F-DOPA PET scan and will instead move to event monitoring.
2. ¹⁸F-DOPA post-injection assessment: done approximately 15-20 minutes post injection of ¹⁸F-DOPA and if AE observed a second AE assessment is required ≤24 hours post injection.
3. All follow-up serial imaging after initial treatment until progression up to 5 years. Note a typical grade IV follow-up schedule will include follow-up scans every 2 months for the first year after

radiation therapy, every 3 months for the second year, every 4 months for the third year, every 6 months after that. The actual timing of the follow-up scans for an individual patient will be per the clinician's discretion, e.g. if the clinician suspects possible progression, they may schedule more frequent follow-up imaging. While it is extremely unlikely (as current time to progression is 6 to 9 months), if a grade IV patient did not progress for 5 years, they may have up to 16 follow-up visits.

4. Patient will complete a maximum of 6 post-baseline QOL/MMSE evaluations
 5. Post RT scans to occur 3 to 6 weeks after RT is complete, to coordinate with first follow-up appointment
 6. Pre-treatment measurement
 7. For patients who have had a 3T glioma protocol MR scan post-operatively at this institution prior to consenting for this study, research funds will be used to repeat the advanced MR scans prior to RT for this study.
 8. Must be done ≤ 14 days prior to start of RT
 9. CT simulation can be done prior to or after registration.
 10. Max grade of Adverse Events experienced during RT to be recorded at the end of RT.
 11. To be assessed by Radiation Oncologist at baseline and during RT, and Medical Oncologist for Cycle 2 and subsequent cycles.
 12. Baseline MMSE, QOL, Concurrent Steroids and Anticonvulsants assessments can occur prior to registration and are to be completed prior to the first ^{18}F -DOPA injection.
 13. MGMT Testing Results can be submitted at any time prior to, or after, registration.
- R Research funded (see Section 19.0)

5.0 Grouping Factors:

Group 1: Grade IV patients vs.

Group 2: Grade III glioma patients: Note: as of addendum 8, Grade III patients are no longer being enrolled.

6.0 Registration/Randomization Procedures

6.1 To Register a Patient

To register a patient, access the Mayo Clinic Cancer Center (MCCC) web page and enter the registration/randomization application. The registration/ randomization application is available 24 hours a day, 7 days a week. Back up and/or system support contact information is available on the Web site.

If unable to access the Web site, call the MCCC Registration Office at [REDACTED] between the hours of 8 a.m. and 4:30 p.m. Central Time (Monday through Friday).

The instructions for the registration/randomization application are available on the MCCC web page [REDACTED] and detail the process for completing and confirming patient registration. Prior to initiation of protocol treatment, this process must be completed in its entirety and a MCCC subject ID number must be available as noted in the instructions. It is the responsibility of the individual registering the patient to confirm the process has been successfully completed prior to release of the study agent. Patient registration via the registration/randomization application can be confirmed in any of the following ways:

- Contact the MCCC Registration Office [REDACTED]. If the patient was fully registered, the MCCC Registration Office staff can access the information from the centralized database and confirm the registration.

- Refer to “Instructions for Remote Registration” in section “Finding/Displaying Information about A Registered Subject.”

6.2 IRB Approval

Documentation of IRB approval must be on file in the Registration Office before an investigator may register any patients.

In addition to submitting initial IRB approval documents, ongoing IRB approval documentation must be on file (no less than annually) at the Registration Office (fax: [REDACTED]). If the necessary documentation is not submitted in advance of attempting patient registration, the registration will not be accepted and the patient may not be enrolled in the protocol until the situation is resolved.

When the study has been permanently closed to patient enrollment, submission of annual IRB approvals to the Registration Office is no longer necessary.

6.3 Verification prior to registration

Prior to accepting the registration, the remote registration application will verify the following:

- IRB approval at the registering institution
- Patient eligibility
- Existence of a signed consent form
- Existence of a signed authorization for use and disclosure of protected health information

6.4 Radiation therapy on this protocol must be performed at Mayo Clinic Rochester, Northfield, LaCrosse, Mankato, Eau Claire, or Albert Lea under the supervision of a radiation oncologist.

6.5 Tests and procedures (Section 4.0) must be completed within the guidelines specified on the test schedule.

6.6 Patients may be registered by the treating physician or healthcare provider.

6.7 Patient questionnaire booklet is available on site; copies are not acceptable for this submission.

7.0 Protocol Treatment

7.1 CT simulation

The patient will be immobilized and a CT dataset acquired of the patient for treatment planning as per standard of care during the CT simulation appointment.

7.2 PET Scanning

7.21 Timing of PET scanning:

PET scans will be acquired prior to and after completion of radiotherapy. The PET scan to be used for radiation treatment planning should be acquired no more than 14 days prior to beginning radiation treatments. The post-RT PET scan should be acquired 3-6 weeks after completing radiation treatments, to correspond with the first follow-up appointment. Follow-up PET scans will also be acquired at each clinically indicated appointment per the standard of care follow-up regimen at Mayo Clinic Rochester until progression (up to 5 years).

7.22 Patient preparation for PET scan:

A negative urine pregnancy test must be done ≤ 48 hours prior to each ^{18}F -DOPA injection for women of child-bearing potential only. For a positive pregnancy test prior to any post-RT ^{18}F -DOPA injection, the patient will not undergo the ^{18}F -DOPA PET scan and will instead move to event monitoring.

Patients will be instructed to follow a four hour food fast prior to the ^{18}F -DOPA PET scan. Liberal hydration 24 hours before the exam will be encouraged.

Carbidopa, used for Parkinson's patients to inhibit decarboxylation of the ^{18}F -DOPA tracer, is not necessary for brain tumor imaging.

7.23 ^{18}F -DOPA PET:

A total of $5.0 \pm 10\%$ mCi of ^{18}F -DOPA will be intravenously injected. A scout image will be acquired in order to prescribe the scan range for the image acquisition. CT images will be obtained and used for attenuation correction of the PET data and, at 10 minutes after injection of ^{18}F -DOPA, a 3D PET acquisition will be acquired for no more than 30 minutes. The PET data will also be acquired concurrently in list mode; this data will be used to salvage a scan should the patient move. The PET sinograms will be reconstructed with a fully 3D-OSEM algorithm into a 300 mm field of view with a pixel size of 1.17mm and slice thickness of 1.96mm. All images will be transferred to a Radiation Oncology workstation.

7.3 Advanced MRI Scanning

7.31 Screening for advanced MR eligibility:

The subject will undergo MRI screening for contraindications to scanning and contrast agent administration as per routine clinical protocol at Mayo Clinic.

7.32 Timing of advanced MR scanning:

Advanced MRI will be acquired at the time of the standard CE-MRI examination on a 3.0 Tesla field strength scanner, no more than 14 days prior to beginning radiation treatments, 3 to 6 weeks after completing radiation treatments (corresponding with the first follow-up appointment), and for all follow-up serial imaging after final RT treatment until progression (up to 5 years). The estimated

additional time of advanced MRI (Perfusion MRI and Diffusion Tensor Imaging) will be approximately 10 minutes).

7.33 **Perfusion MRI:**

The pMRI DSC acquisition will be acquired as per standard perfusion DSC clinical protocol of the Radiology Department at Mayo Clinic. The DSC acquisition time is approximately 3 minutes.

The single dose of Gd-based contrast agent gadobutrol (Gadavist) (0.10 mmol/kg) to be administered for each MR exam is current standard of care for the Radiology Department at Mayo Clinic. Recent literature has linked the development of a condition called Nephrogenic Systemic Fibrosis (NSF) with administration and dosage of Gd-based contrast agents in patients with renal failure or insufficiency. Per standard of care at Mayo Clinic, we will screen all patients for renal failure/insufficiency to ensure normal renal function. There have been no reports in the literature of the occurrence of NSF in patients with normal renal function [62, 69].

7.34 **Diffusion MRI:**

DTI data will be acquired as per standard DTI clinical protocol of the Radiology Department at Mayo Clinic.

7.4 Radiation Treatment

7.41 **Target delineation:**

Following informed consent and co-registration of the PET and MRI datasets with the planning CT acquired during the standard of care CT simulation appointment, the radiation oncologist will define the target volumes to use for radiation treatment planning. The pre-RT ^{18}F -DOPA PET scan and standard of care MRI will be co-registered with the treatment planning CT.

Target delineation will be based both on MRI and PET imaging, defining each gross tumor volume (GTV), clinical target volume (CTV), planning target volume (PTV) and associated dose as in [Table 1](#). The MR criteria used in the definition of GTV5100_MR and GTV6000_MR will be identical to the historical standard of care at Mayo Clinic and NCCTG, but volumes encompassing both low and high signal PET disease (GTV5100_PET) and only high signal PET disease (GTV6000_PET) will also be included in the treatment volumes. GTV5100_MR, GTV5100_PET, GTV6000_MR and GTV6000_PET will be expanded by 1 cm to accommodate sub-clinical disease spread, modified per MD discretion as needed (see [Figure 8](#)). These CTVs will then be combined for each dose level, and CTV5100 and CTV6000 will be expanded by 0.3 cm to accommodate random setup uncertainty. These expansion values and doses being delivered to PTV5100 and PTV6000 conform to the Mayo standard of care and are the same expansion definitions used in NCCTG clinical trials N0177, N057K, N0874 and N0877.

Beyond these standard treatment doses, we plan to boost the MR- and PET-defined high density disease (GTV7600=GTV6000) with no expansion for sub-clinical disease to a total dose of 76 Gy. Boost volumes will be based on post-operative ^{18}F -DOPA imaging. For patients that also were included on the corresponding neurosurgical trial (MC1373), post-operative ^{18}F -DOPA will be required for any patients that have undergone any surgical procedure other than biopsy only.

Delineation of normal structures should follow the “Contouring CNS and Head and Neck” in [Appendix V](#).

[figure not shown]
Table 1. Target delineation for MRI and PET Imaging

Dose	GTV/CTV/PTV definition:	GTV_MR definition:	GTV_PET definition:
51 Gy	$GTV5100 = GTV5100_MR + GTV5100_PET$ $CTV5100_MR = GTV5100_MR + 1\text{ cm}$ (modified as needed) $CTV5100_PET = GTV5100_PET + 1\text{ cm}$ (modified as needed) $CTV5100 = CTV5100_MR + CTV5100_PET$ $PTV5100 = CTV5100 + 0.3\text{ cm}$	$GTV5100_MR = \text{Boolean}(T1_GAD \pm FLAIR) \pm T1_Cavity$	$GTV5100_PET = \text{gold_PET}$
60 Gy	$GTV6000 = GTV6000_MR + GTV6000_PET$ $CTV6000_MR = GTV6000_MR + 1\text{ cm}$ (modified as needed) $CTV6000_PET = GTV6000_PET + 1\text{ cm}$ (modified as needed) $CTV6000 = CTV6000_MR + CTV6000_PET$ $PTV6000 = CTV6000 + 0.3\text{ cm}$	$GTV6000_MR = \text{Boolean}(T1_GAD \pm T1_Cavity)$	$GTV6000_PET = \text{Boolean}(HGG\text{ Threshold and gold_PET})$
76 Gy	$GTV7600 = GTV7600_MR + GTV7600_PET$ $CTV7600_MR = GTV7600_MR + 0\text{ cm}$ $CTV7600_PET = GTV7600_PET + 0\text{ cm}$ $CTV7600 = CTV7600_MR + CTV7600_PET$ $PTV7600 = CTV7600 + 0.3\text{ cm}$	$GTV7600_MR = GTV6000_MR$	$GTV7600_PET = GTV6000_PET$

Table 1: Radiotherapy doses and definitions of the volumes to be targeted with those doses, with the gold_PET contour reviewed and approved by either [REDACTED] or [REDACTED], and the HGG Threshold contour derived from a tumor to normal brain ratio (T/N)>2.0 determined initially from preliminary studies ([Figure 5](#)).

7.42 Treatment planning and delivery:

Patients will receive intensity modulated RT delivered over 30 fractions with either photons or protons per MD discretion, with concurrent and adjuvant TMZ.

GTV5100= 51Gy (in blue dashes) CTV5100= GTV5100 + 1cm PTV5100= CTV5100 + 0.3cm
 
GTV6000= 60Gy (in yellow dashes) CTV6000= GTV6000 + 1cm PTV6000= CTV6000 + 0.3cm
 
GTV7600= 76Gy (in yellow dashes) CTV7600= GTV7600 + 0cm PTV7600= CTV7600 + 0.3cm
	
GTV5100_MR= Boolean (T1_GAD + FLAIR) + T1_Cavity GTV5100_PET= gold_PET GTV5100= Boolean (GTV5100_MR + GTV5100_PET)
 
GTV6000_MR= Boolean (T1_GAD + T1_Cavity) GTV6000_PET= Boolean (HGG_threshold and gold_PET) GTV6000= Boolean (GTV6000_MR + GTV6000_PET)
 
GTV7600= GTV6000


CTV5100_MR=GTV5100_MR + 1CM (modified as needed) CTV5100_PET=GTV5100_PET + 1CM (modified as needed) CTV5100= GTV5100 + 1cm, then Boolean (CTV5100 and brain) or CTV5100_MR + CTV5100_PET
 
CTV6000_MR=GTV6000_MR + 1CM (modified as needed) CTV6000_PET=GTV6000_PET + 1CM (modified as needed) CTV6000= GTV6000 + 1cm, then Boolean (CTV6000 and brain) or CTV6000_MR + CTV6000_PET
 
CTV7600= GTV7600 + 0 cm, then Boolean (CTV7600 and brain)
	
PTV5100 = CTV5100 + 0.3cm PTV6000 = CTV6000 + 0.3cm PTV7600 = CTV7600 + 0.3cm
 
*Need to evaluate T1_GAD volume outside FLAIR and determine if real or to exclude
 
*Need to evaluate inclusion or exclusion of small GTV6000_PET volume at a considerable distance from bulk T1_GAD and bulk GTV6000_PET
 
*Need to make sure GTV6000_PET does not exceed GTV5100_PET
 
*Need to make sure all CTVs are inside the brain tissue contour
 
*Need to evaluate inclusion or exclusion of small PTV volumes at a considerable distance from bulk CTV volumes

Figure 8: Depiction and details for generating GTV, CTV and PTV volumes

7.5 Follow-up protocol

7.51 **Response Assessment:**

Post-treatment tumor recurrence will be monitored through follow-up imaging, using standard of care MRI to assess tumor response based on the Response Assessment in Neuro-Oncology (RANO) Working Group criteria until progression of disease (up to 5 years) [70].

7.52 **Patterns of Failure:**

For those who recur, follow-up imaging at progression will be co-registered with pre-treatment imaging in MIM Maestro™, and patterns of failure will be analyzed in the Eclipse treatment planning software (Varian Medical Systems, Palo Alto, CA) by determining the portion of the recurrence volume (RecVol) that falls within the 95% isodose line of the boost dose from the delivered RT plan and classifying each recurrence as either ‘central’ (>95%), ‘in field’ (80 - 95%), ‘marginal’ (20 - <80%), or ‘distant’ (<20%).

7.53 **Follow-up Imaging:**

Once the full course of radiotherapy is complete, an ¹⁸F-DOPA-PET scan will be obtained in addition to the standard of care MRI along with state-of-the-art pMRI and DTI sequences, to use as a baseline for follow-up imaging. ¹⁸F-DOPA PET imaging has been demonstrated to differentiate recurrence from pseudo-progression [6, 9]. Accordingly, at every standard of care glioma follow-up imaging regimen appointment scheduled at Mayo Clinic Rochester until progression (up to 5 years), in addition to standard of care MRI, an ¹⁸F-FDOPA-PET scan as well as perfusion MRI and DTI sequences will be obtained. pMRI and DTI sequences will be compared against ¹⁸F-DOPA PET data to evaluate earliest accurate differentiation of tumor progression versus treatment response.

7.54 **Outcomes:**

Outcomes for patients treated prospectively with the addition of ¹⁸F-DOPA PET image-guided dose escalation will be determined and compared against patients treated at Mayo Clinic on NCCTG trials as described in Sections [7.41](#) and [16.11](#).

7.55 **Acute and Late Toxicity Monitoring:**

Using the dose escalation approach described above, previous studies have successfully dose escalated to 76 – 80 Gy without significant increases in acute or late adverse effects [51]. Nonetheless, both acute (available at <http://ctep.cancer.gov>) and late [71] toxicity will be monitored continuously as each patient is accrued and follow-up data are accumulated, and the PTV3 dose level will be adjusted if necessary.

7.6 **Quality of life – patient reported outcome:**

Quality of life (QOL) will be compared to high-grade glioma patients treated on previous Radiation Therapy Oncology Group (RTOG) protocols. QOL and cognitive function will be evaluated with the MD Anderson Symptom Inventory Brain Tumor Module (MDASI-BT) and Mini-Mental Status Exam (MMSE) questionnaires. Every patient will be asked to complete the whole form packet at baseline and at each MRI evaluation for a maximum of 6 evaluations. These time points are selected to capture the quality of life profile and correlate findings with radiologic and clinical progression as well as time points used on prior studies to allow historical comparisons.

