[76]. Time to disease progression is defined as the time from initial surgery to the earliest date documenting confirmed-progression. If a patient dies without documentation of disease progression, the patient will be considered to have had tumor progression at the time of death. If a patient is declared to be a major treatment violation, the patient will be censored on the date the treatment violation was declared to have occurred. In the case of a patient starting treatment and then never returning for any evaluation, the patient will be censored for progression on the last day of therapy. This analysis will be conducted split by MGMT-methylation status of the patients and historical control.

16.323 Overall Survival

Compare patient outcomes including overall survival after radiation therapy targeting volumes designed with both ^{18}F -DOPA PET and conventional MR image information with historical controls from Mayo Clinic Rochester patients. As described above for confirmed-progression free survival, we will analyze both historical control patients and our prospective dose escalation patients for overall survival. Survival time is defined as the time from initial surgery to death due to any cause. The distributions of survival times and comparisons between these two groups will be estimated using the method of Kaplan-Meier [76].

16.324 Quality of Life

Evaluate quality of life after radiotherapy treatment targeting dose escalated volumes defined to include high ^{18}F -DOPA PET uptake. Quality of life (QOL) will be compared to high-grade glioma patients treated on previous North Central Cancer Treatment Group protocols. QOL and cognitive function will be evaluated with the MD Anderson Symptom Inventory Brain Tumor Module (MDASI-BT) and Mini-Mental Status Exam (MMSE) questionnaires at baseline and at each MRI evaluation up to 6 evaluations to capture the quality of life profile and correlate findings with radiologic and clinical progression as well as time points used on prior studies to allow historical comparisons. The main QOL analysis will be the change from baseline to first subsequent MRI timepoint in the overall score from the MDASI-BT. All other QOL analysis will be exploratory and may include change percent from baseline to all timepoints using t-tests and generalized linear models to test for changes at each time point and non-zero slope respectfully.

16.325 Adverse Events

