Registration. Ask the patient if you may test his/her memory. Then name three unrelated objects, clearly and slowly, about a second for each. After you have said all three, ask the patient to repeat them. This first repetition determines the score. Score one point for each repeated object (0 – 3). If the patient does not repeat all three objects, the tester should repeat the objects (up to a maximum of six times) until the patient can say all three. In cases where a patient cannot learn all three objects in six trials, recall (see below) cannot be meaningfully tested.

When registration is complete, tell the patient, “Try to remember them because I will ask for them in a little while.”

Attention and Calculation. Ask the patient to begin with 100 and count backwards by seven. Stop after five subtractions (93, 86, 79, 72, 65). Score the total number of correct answers. If the patient will not perform this task, ask him or her to spell the word “WORLD” backwards. The score is the number of letters in correct order (e.g., DLROW – five, DLORW – three).

Recall. Ask the patient if he/she can remember the names of the three objects learned in the Registration section. Give one point for each correct answer.

Language. There are six operations in this section.

Naming. Show the patient a wrist watch and ask him/her what it is. Repeat for a pencil. Give one point for each correct naming (0 – 2).

Repetition. Have the patient repeat, “No, ifs, ands, or buts”. All only one trial. Given one point for a completely correct repetition.

Three-Stage Command. Place a piece of blank paper in front of the patient and say; “Take this paper in your right hand. Fold the paper in half. Put the paper on the floor”. Give one point for each correctly performed command.

Reading. Show the patient the page with the sentence “Close your eyes” (page 2). Ask the patient to read it and do what it says. Since this is not a memory task, the tester may prompt the reader to “do what it says” after the reader reads the sentence. Score one point if the patient actually closes his or her eyes.

Writing. Give the patient the page with the word sentence (page 3) and ask him/her to write a sentence for you. Do not dictate a sentence; it is to be written spontaneously. The sentence should contain a subject and a verb, and should make sense. Ignore minor spelling or minor grammatical errors when scoring. Score one point for a correct sentence.

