Appendix IV MDASI - BT

Date: _____

Institution: _____

Participant Initials: _____

Hospital Chart #: _____

Participant Number: _____

M. D. Anderson Symptom Inventory - Brain Tumor (MDASI - BT)

Part I. How **severe** are your symptoms?

People with cancer frequently have symptoms that are caused by their disease or by their treatment. We ask you to rate how severe the following symptoms have been *in the last 24 hours*. Please fill in the circle below from 0 (symptom has not been present) to 10 (the symptom was as bad as you can imagine it could be) for each item.

	Not Present 0	1	2	3	4	5	6	7	8	9	As Bad As You Can Imagine 10
1. Your pain at its WORST?											
2. Your fatigue (tiredness) at its WORST?											
3. Your nausea at its WORST?											
4. Your disturbed sleep at its WORST?											
5. Your feeling of being distressed (upset) at its WORST?											
6. Your shortness of breath at its WORST?											

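### Sections 7.6 and 16.324 name different historical groups for the quality-of-life comparison, and the exploratory analyses allow percent change on a scale where zero is a valid baseline

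*Combined protocol and SAP*

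**What the plan says.** QOL is a secondary goal. Goal 2.23 reads, in part, "Evaluate quality of life after radiotherapy treatment targeting dose escalated volumes defined to include high" tracer uptake, and it names no comparison group.

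Two later sections do name one. Section 7.6: "Quality of life (QOL) will be compared to high-grade glioma patients treated on previous Radiation Therapy Oncology Group (RTOG) protocols". Section 16.324: "Quality of life (QOL) will be compared to high-grade glioma patients treated on previous North Central Cancer Treatment Group protocols". Both sections use the MDASI-BT and the MMSE, and both justify the assessment times partly by the wish to match earlier studies.

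Section 16.324 then sets the order of the analyses. "The main QOL analysis will be the change from baseline to first subsequent MRI timepoint in the overall score from the MDASI-BT". The next sentence covers the rest: "All other QOL analysis will be exploratory and may include change percent from baseline to all timepoints using t-tests and generalized linear models". The t-tests are for change at each time point and the generalized linear models are for a non-zero slope. No correlation structure is given, and no rule for a baseline of zero.

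Appendix IV scores MDASI-BT symptom items "from 0 (symptom has not been present) to 10". Section 4.0 allows up to six evaluations per patient after baseline.

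**The concern.** The study has one arm, so a historical group is the only external reference for QOL. With two groups named and neither described further, the choice can be made after the data are seen. It also cannot be checked whether the chosen patients completed the same instruments at comparable times, which is the stated reason for the schedule.

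Percent change fails in a different way. A patient who reports a symptom as absent at baseline has no percent change at all, and a patient with a very low score can show a very large one. An average of such values depends on how zeros are handled and on a few low baselines. For a single item, a patient at zero can only stay the same or worsen, so omitting zeros would leave out newly arising symptoms.

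Finally, a slope fitted to several scores per patient needs a model that recognises which scores belong to the same patient. The text does not say that it will.

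**Working it through.** The plan states no QOL sample size, power, effect size or standard deviation, so there is no figure to reproduce. The first and last steps compare texts; the middle two are arithmetic.

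**1. Which comparator?**

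- Section 7.6: patients on earlier RTOG protocols.
- Section 16.324: patients on earlier NCCTG protocols.
- Goal 2.23: none named.
- Goals 2.1, 2.21, 2.22 and 2.25 to 2.27: Mayo Clinic Rochester patients, including those on NCCTG trials.
- Section 7.54 (outcomes): Mayo patients on NCCTG trials.
- Section 16.1: Mayo patients given standard treatment or treated on N057K or N0874.

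Sections 7.6 and 16.324 are both current text and cannot both be followed as the single comparison. RTOG as a historical control group appears only in 7.6, so internal consistency favours 16.324. Section 16.1 says the historical trials had the same MR follow-up regimen and recorded toxicity. It does not say that they collected the MDASI-BT or the MMSE. Whether a usable historical group exists is therefore open under either name.

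**2. Percent change at low baselines.** With baseline B and follow-up F, percent change = 100 × (F − B) / B. For a 1-point worsening, F = B + 1:

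| Baseline B | Absolute change | Percent change |
|---|---|---|
| 0 | 1 | undefined |
| 0.5 | 1 | 200% |
| 1 | 1 | 100% |
| 2 | 1 | 50% |
| 5 | 1 | 20% |

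A composite score is zero only if every contributing item is zero, but low composites are still unstable. Neither 7.6 nor 16.324 defines the overall score. If it were the mean of the 22 symptom items (assumption), a patient whose only symptom moved from 1 to 2 would go from 1/22 to 2/22. That is a 100% worsening for an absolute change of 1/22 = 0.045 points.

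**3. How often would it be undefined?** The proportion p with a zero baseline is not in the documents, so a range is assumed. The chance of at least one undefined value among n patients is 1 − (1 − p)^n. The values of n are 45 (primary-endpoint sample, 16.21), 72 (minimum Grade IV sample for the correlative endpoints, 16.33) and 93 (maximum registered, 16.22):

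| p (assumed) | n = 45 | n = 72 | n = 93 |
|---|---|---|---|
| 1% | 0.36 | 0.52 | 0.61 |
| 2% | 0.60 | 0.77 | 0.85 |
| 5% | 0.90 | 0.98 | 0.99 |
| 10% | 0.99 | >0.99 | >0.99 |

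If 30% of patients scored a single item 0 at baseline (assumption), 0.30 × 72 = 21.6, so about 22 of 72 would have no percent change for that item.

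**4. Slope.** Each patient can contribute several scores. A generalized linear model can handle this with GEE or a random effect, but 16.324 names neither. This is missing detail, not a stated assumption of independence.

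**The case against.** The strongest reply is that little depends on any of this. The main QOL analysis is a within-patient change score that needs no comparator and is not a percentage. Everything else is labelled exploratory, and percent change is only something that may be done. The historical QOL comparison has no values, test or decision rule attached. All of that stands and limits the size of the point. It does not remove the contradiction or supply a rule for zero baselines.

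A reader might infer more than the documents support:

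- *That the QOL conclusion would change with the section followed.* No historical QOL data are given for either group, so this cannot be shown.
- *That toxicity of the boost is understated.* Toxicity is a separate endpoint, graded by CTCAE v4.0 and RTOG/EORTC criteria (16.325). The plan does not say that zero-baseline patients are dropped. Even within the exploratory analysis the direction is not settled, because low baselines can inflate apparent worsening.
- *That standard errors are wrong by a known factor.* With six scores and an assumed correlation of 0.5, the variance factor for a pooled mean is 1 + 5 × 0.5 = 3.5. No planned analysis is such a mean: the t-tests use one change per patient at each time point. For a slope, ignoring the correlation usually makes the standard error too large.
- *That the zero-baseline problem carries over to cognition in the same form.* The MMSE is scored out of 30, with higher scores better; the 0 to 10 scale belongs to the MDASI-BT.
- *That the MMSE form drops a subtraction.* The Appendix II instructions say "Stop after five subtractions (93, 86, 79, 72, 65", while the form lists 100, 93, 86, 79, 72 for 5 points. Read as the five numbers from which 7 is subtracted, the form gives the same five answers.

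**Conclusion.** The point holds in limited form. Two current sections give incompatible comparison groups for one secondary endpoint, and they must be reconciled before the historical comparison can be done. This rests on the text alone. Aligning 7.6 with 16.324 rests on NCCTG and Mayo patients being the comparator elsewhere. It also depends on historical patients having the instrument data, which the documents do not establish.

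Percent change is a poor choice for the MDASI-BT: undefined at zero, and for the same 1-point worsening five times as large at a baseline of 1 as at 5. How many patients this touches depends on the assumed proportion at zero. The missing within-patient term is a smaller gap in the same exploratory paragraph. The main QOL analysis is not affected.

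**What to change.** Change the wording in two places.

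- **Section 7.6:** replace the RTOG reference so that it matches 16.324. In both sections, identify the historical trials and limit the comparison to patients with the same instrument at matching times. If there are none, delete the historical QOL comparison and report within-patient change only.
- **Section 16.324:** replace percent change by absolute change from baseline, as the main QOL analysis already does. State that the slope will be estimated with a within-patient term, by a mixed model or GEE.

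The cost is an edit to two sections and a check of which historical trials hold the instrument data. No new data are collected from patients, and neither the sample size nor the main QOL analysis changes.
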